- Yung, A. R., Phillips, L. J., Yuen, H. P., & McGorry, P. D. (2004). Risk factors for psychosis in an ultra highrisk group: psychopathology and clinical features. *Schizophr Res*, 67(2-3), 131-142.
- Yung, A. R., Stanford, C., Cosgrave, E., Killackey, E., Phillips, L., Nelson, B., et al. (2006). Testing the Ultra High Risk (prodromal) criteria for the prediction of psychosis in a clinical sample of young people. Schizophr Res, 84(1), 57-66.
- Yung, A. R., Yuen, H. P., Berger, G., Francey, S., Hung, T. C., Nelson, B., et al. (2007). Declining Transition Rate in Ultra High Risk (Prodromal) Services: Dilution or Reduction of Risk? *Schizophr Bull*.
- Yung, A. R., Yuen, H. P., McGorry, P. D., Phillips, L. J., Kelly, D., Dell'Olio, M., et al. (2005). Mapping the onset of psychosis: the Comprehensive Assessment of At-Risk Mental States. *Aust N Z J Psychiatry*, 39(11-12), 964-971.

Appendices

a) Further details on the potential progression to the full trial

We suggest that the suitability for progression to a substantive trial should depend on whether the data collected in the early phase of the present study meets specific objectives for recruitment and suitability criteria. These are: a) If recruitment within the first year of the present study is within 20% of planned; b) if the assessments achieved are judged as suitable and the data of high quality; c) if the qualitative study suggests inclusion criteria and procedures are appropriate; d) if the intervention is well received; e) if we are not excluding potentially important subgroups and f) if there are no other substantial changes to the present protocol we would regard the data collected in the pilot phase as suitable for inclusion in a substantive trial as an internal feasibility phase.

A substantive proportion, if not all, pilot data which would be collected during the present project may then be suitable to be used as an internal feasibility phase of a substantive trial. We have increasing confidence that we can complete a successful trial, however, it is sensible to be prudent. We therefore suggest that the decision about suitability for including pilot data within any future substantive trial and the progression to such a trial should be dependent on checking the results of the proposed qualitative study and the quality of the empirical data collected in the early phase of this project against the above criteria. This data and the criteria can then inform the decision making of the Trial Steering Committee (TSC) who will make the decision on progression in liaison with the Data Monitoring and Ethics Committee (DMEC) and the Service User Advisory Committee (SUAC) and review this at key decision points in the milestones. We highlight a decision making and research governance process, and potential progression below and suggest specific milestones later in the protocol.

PRODIGY Protocol: Version 4 (18/01/2013)

By the end of year 1 of the study we aim to complete the qualitative project and recruit at least 40 participants: 20 treatment and 20 controls and complete baseline assessments and a 3 month follow up. At 12 months we plan to examine this data and evaluate the suitability of progressing to a substantive trial using the data collected as an internal feasibility stage of a substantive trial. In months 13 and 14 a decision will be made by the Trial Steering Committee who will assess the data collected with respect to the criteria above, and will consult with the DMEC and the Service Users Advisory Committee (SUAC) to decide whether the data is a) suitable for inclusion as the internal feasibility phase of a substantive trial; or b) whether it would be best to complete the study as an external pilot; c) whether to change or adapt the protocol and then to continue recruitment or d) to stop the project.

- a) If the decision is to proceed to a substantive trial using the pilot data as an internal feasibility pilot. We would continue to collect data following the present protocol. But at the same time aim to proceed to present to HTA by month 18 a fast track full trial application which will include the data on recruitment and retention in the pilot study. This would allow decision on an extension to the present project to complete a substantive trial involving inclusion of two extra centres in the West Midlands (Birmingham and Coventry). This would keep the team and procedures together while continuing to recruit a further 60 participants over the subsequent 18 months and awaiting a decision on further funding. This also allows the possibility of analysing the data as a stand alone external pilot comparing 50 versus 50 as originally planned if the committee decision is not to fund a full multicentre substantive trial.
- b) If the collective decision by the TSC is not to proceed to a full trial and that instead alterations to the protocol are required. We will then regard the results of the first 40 participants as an external pilot and set this aside and write it up as such, together with the qualitative studies. The TSC would then seek guidance from the DMEC and SUAC and HTA who together with the research team can agree any changes to protocol which may be required. We would then proceed to recruit a further 40 participants over the next 12 months checking again the data against the quality criteria at month 24. If this data is then judged as suitable we would then proceed to proceed submit a full trial application using these cases as an internal feasibility stage while recruiting the final 20 participants to the end of treatment as planned similar to described in a).
- c) If recruitment falls 20% below planned rates at key time points of 12 and 24 months or if procedures are otherwise judged as not feasible by the TSC we will seek advice from the DMEC and the SUAC and HTA as to whether it is most appropriate to stop the project altogether and allow for contracts to expire.

b) Further clarification of the use of the time use assessment interview to assess primary outcomes

In this study we use number of hours per week engaged in structured activity (which includes time spent both constructive economic activity: e.g. work; education, childcare and in structured activity e.g. chores, sports, voluntary work, structured social activity) as our primary outcome assessment of social functioning. We assess time spent in activity using the Time Use Survey (Lader, Short, Gershuny, 2006) which is the standard Time Use interview as used in the Office of National Statistics UK Time Use Survey. The reason for this choice of assessment it that one of the identified problems in undertaking research on social recovery has been the lack of a valid, sensitive and reliable outcome assessment. While there are a number of widely used scales of quality of life and social functioning used with people with mental illness these have several problems. First, such scales often lead to arbitrary definitions of groups based on social functioning or quality of life scores. For example, it has been recently highlighted that identifying groups of young people with severe mental illness as socially impaired on the basis of arbitrary scores on two widely used social functioning scales (the QLS and SOFAS) resulted in group identified as social impaired in which 17% were working full time (Lin et al, 2011). This is contradictory as working full time is often taken as a marker of full social recovery. This may arise from the well recognised problem that many so called social functioning scales often confound symptom assessments (of depression and negative symptoms) with social outcome so that people who make social recoveries despite their symptoms may be wrongly identified. Another problem with many of the present scales of social functioning is that they are relatively insensitive to important clinical changes, and changes in scores difficult to interpret. Defining social outcome based on hours in activity overcomes these issues and provides an assessment with direct face validity to users, clinicians and service managers and commissioners based on hours in constructive economic activity, or structured activity.

The interview assessment is well established and available from the ONS time use survey (Lader, Short, Gershuny, 2006), which itself derived from an extensive research portfolio of studies on time use in the UK and

PRODIGY Protocol: Version 4 (18/01/2013)

internationally. In work carried out as part of our MRC trial platform we showed that the Time Use Assessment shows good reliability with other well known scales of Quality of life and social functioning but is less confounded with symptoms (Fowler et al, 2009). It is also a scale which users and other interested parties find readily and directly understandable. Focus groups of clinicians and users we carried out as part of our MRC trial platform study have reached a consensus agreement that for this population a 4 hour gain in structured activity represent an agreed minimum clinically significant gain. We have shown the scale to be sensitive to change in its use as primary outcome in our MRC trial platform study (ISREP; Fowler et al 2009).

As a result of a series of studies we have completed since the outline proposal was submitted, we now have data which allows comparison of clinical groups of young people with severe mental illness with young people from the general population and provides us with an empirical basis to identify a socially disabled group at risk group we wish to target in a trial. In table 1 we show data on time spend in constructive economic and structured activity comparing different samples of young people with ultra high risk symptoms (from the EDIE II trial) with young people with first episode psychosis (from the National Eden study) with young people with chronic psychosis and social disability (from ISREP) with age matched data from the ONS time use survey which allows a comparison with 6000 age matched young people in the general population. As can be seen the ultra high risk group has a similar relatively low level of activity to the samples, first episode psychosis and even chronic psychosis samples. This is suggestive of the emergence of social disability at an early stage in the evolution of severe mental illness and consistent with long term follow up studies. However, large standard deviations indicate considerable heterogeneity in all the samples showing what a large range of functioning from normal patterns of activity to very low patterns of activity. The group at most risk have early signs of social impairment and have low patterns of activity at an early stage of disorder (Lin et al, 2011). It young people who have severe and complex mental health problems in association with low activity we wish to target.

Our analyses suggest that a useful cut off for isolating a socially disabled group using the Time use Assessment may be performing at a level of less than 30 hours per week total structured activity. As can be seen above this is less than half the mean level of functioning of young people in the normal population. Analyses of the EDIE 2 trial data and referral patterns to our existing clinical services suggest that this is a population of young people who have severe and complex needs which are not met by current interventions, but are a group which are help seeking and already being referred into research trials and clinical services (though often at present excluded). Several recent national reports have highlighted the unmet needs of this population (Singh et al, 2010; DoH, 2008) and our research and clinical experience has already shown we can recruit samples into studies. Our analyses of the MRC EDIE 2 trial data showed that 122/205 (60%) cases in EDIE were functioning at this level with structured activity below 30hrs per week. This subgroup are engaged at a very low level of activity (mean less than 15 hours total structured activity in a week) and they are a more homogeneous sample (Mean 13.96 SD = 8.71). Our established clinical services for detection of cases at risk of psychosis which we successfully used in the completion of the EDIE 2 multicentre trial can therefore provide a large source of the referrals for this study. In addition we also intend to recruit young people who have severe and complex mental health problems and social impairment but who have less severe attenuated psychotic symptoms (and thus were excluded from EDIE 2 and early intervention services as they do not meet symptomatic criteria for an At Risk Mental state or Psychosis). We get many referrals to our existing clinical services of this type. In Norfolk we ran a pilot service for young people aged 14 to 18 which included this group. This clinical pilot has been highlighted as an example of clinical excellence in engaging and treating young people (Joint working at the interface, 2011) and shown that such cases are available for recruitment as they are commonly referred to early detection and intervention services for psychosis (though currently excluded). Also this group includes young people with severe and complex mental health problems who are not in education, employment and training (NEET) who are identified as being at high risk by statutory agencies and are therefore a priority group to target. The group has a similar levels of time use to that of the EDIE 2 sample (mean less than 15 hours, SD 9).

In summary, the Time Use Survey is a well known and validated instrument. We have shown it is acceptable, reliable, and sensitive to change and thus highly suitable to be used as the primary outcome to assess social functioning levels in a randomised controlled trial involving young people with severe and complex mental health problems and social impairment.

	Constructive Economic	Structured
		(without hobbies)
EDIE Young people with Ultra high risk symptoms (N = 288)	25.11 (27.05)	30.67 (27.81)
EDEN Young people with first episode psychosis (N = 1027)	17.23 (23.80)	25.44 (27.10)
ISREP Young people with chronic psychotic disorder and social impairment	12.43 (17.05)	19.66 (17.54)
(N = 77)		
ONS Aged matched young people in the normal population (N = 6000)	50.93 (25.40)	64.18 (27.22)

Table 1. Comparison of Constructive Economic and Structured Time Use across studies – Mean hours per week (SD)

Note. Constructive Economic Activity = work, education, voluntary work, childcare & chores

Structured Activity = Constructive Economic Activity plus leisure and sports activities

c. Further detail regarding the proposed qualitative study

The proposed methods for collecting qualitative data from young people draw on earlier studies of young people's experiences of mental health services and participating in research. These studies have highlighted the importance of flexible data collection processes; of researchers being skilled in engaging with and working at the pace of young people often presenting with multiple difficulties and complex care histories (Street & Svanberg 2003), of the ethical implications of researching vulnerable young people (Taylor et al 2010), and of being able to work across and gather information from a range of different agencies (Garcia, Vasiliou & Penketh 2007). Studies have suggested the importance of service user involvement in understanding the views of those with emergent signs of severe mental illness (Hardy, Dickson, & Morrison, 2009) and in this study, we intend to involve service users at all project stages as much as possible.

A qualitative approach is particularly suited to taking the viewpoints of young people. Interpretative Phenomenological Analysis is the method chosen for the proposed research, as it is focused specifically on the individual experiences contextualised within an understanding of young peoples' own lifeworlds. This approach had been successfully adopted by comparable studies, seeking participant views of early intervention services (O'Toole, et al. 2004). These and other research studies involving young people have also drawn attention to the importance of providing young people with detailed but accessible information about the study what it entails, its aims, how confidentiality will be protected and how findings will be used. All of these issues have been fully accounted for in our approach.

Data gathered from the qualitative sub-study of the pilot RCT will inform suggestions about improvements and alterations to the recruitment techniques, measures and tools utilised as part of the study, and may potentially suggest alterations to the CBT intervention. A further outcome of the qualitative sub-study will be to define the sampling frame for the larger embedded qualitative study planned as part of the future RCT, by analysing variability across the recruited pilot sample. The pilot qualitative study will begin to explore experiences of the intervention, thereby suggesting major themes for exploration at interview in the embedded qualitative study of the larger RCT. Further details are supplied below.

d) Further justification of selection of age bands and consider the ethical implications of recruiting children and young people

We will recruit only young people aged 16 and above. This is appropriate our experience suggests that young people aged above 16 would be most suitable for this intervention and the assessments we plan to use are validated for use with over 16 year olds. Also, our analysis of the current numbers of young people aged under 16 being referred to our existing services (which have a catchment of 14 to 35) indicate that the numbers of children we could identify as being at risk using the present criteria below this age would be very low.

Our approach to recruitment, conducting assessments and carrying out intervention has carefully considered the ethical implications of this study. The specific adaptations we have made include the need for a flexible approach; to use researchers trained and experienced in engaging with and working at the pace of young people with mental health problems; to ensure that all information materials about the study are 'young person friendly' and are accessible to them and their parents and carers. Particular attention will be paid to gaining consent for their involvement in the study. A detailed research pack including information sheet and consent forms will be given to the young person by a member of staff familiar/already working with them, e.g. their care coordinator. This staff member will liaise with the research team regarding the young person's capacity to give informed consent and seek consent from a person with Parental Authority should this be required. The pack will explain the benefits and known risks of the study and will emphasise that the young person's involvement in the study is entirely voluntary, will not affect the treatment and care offered to them in any way and that they can withdraw from the study at any time. A research assistant carefully trained in procedures for eliciting informed consent will work with the care coordinator throughout this process.

All assessments will be conducted in appropriate and accessible venues that suit the needs and preferences of the young people. They will be scheduled at times convenient to the young person and if they wish, a family member, trusted friend or member of staff already known to the young person, can be present to support them if they wish. Young people will also be given the opportunity to comment on the write-up of their interview and will be reassured by the researcher that in all study outputs, data will be written up in such as way as to ensure that neither they nor their family can be identified.

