Target population: Young people aged between 16-25 presenting with persisting signs of social disability operationally defined as engaged in less than 30 hours structured activity per week and who are presenting to youth services in East Anglia and Manchester. They will also be presenting with either a). Attenuated symptoms of psychosis which meet criteria for an at risk mental state, or b). less severe attenuated psychotic symptoms and the presence of severe and complex mental health problems operationally defined by a score of less than 50 on the Global Assessment of Functioning (GAF) score. All potential referrals will be screened first with GAF

score, then activity levels will be checked by the Time Use Survey and symptoms assessed by the Comprehensive Assessment of At Risk Mental States (CAARMS).

Project timetable: The study will take place over 2.5 years (30 months). This involves a 15 month recruitment period in which we can realistically expect a rate of 3-4 participants randomised per month in each site. Given this rate of recruitment, we can expect to recruit to target to meet the 50 participants required from each site. Each participant will have a 9 month intervention and six month follow up. Recruitment will be monitored continuously via an independent DMEC.

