At months 24 to 30: there will either be a repeat of the decision making and preliminary pilot stage as above for the second phase pilot. Or a decision will have been made to continue with data collection as the internal pilot for a substantive trial in which case a submission to HTA for a fast track full trial will be made at 18 months with data continuing in the present study till month 30 which will allow time for the team to continue with the project until a decision on funding is made.

At month 30: the project data collection will finish and depending on the decisions of the above committees according to the qualitative and quantitative data. The data will either be written up as a substantive pilot project involving 100 cases, as a series of external pilots of 40 and 60 cases respectively or it will be the first phase of a larger trial which will continue with another centre depending on power calculation.

14. Team expertise: This project draws together a team of investigators who have considerable experience in designing, running and utilising complex pilot studies of this type. The applicants have considerable experience of working together on previous projects and have established track records in engaging young people in research, and developing innovative psychological interventions.

15. Service Users: We have consulted service users in the course both of preparation of the outline and the full proposal, and we are also planning considerable input to the main study. In the course of preparing the outline and full proposal, we consulted service users in the Norfolk Early Intervention Service regarding the study, focusing especially on the feasibility and acceptability of the intervention and how best to implement it. The main topics in our consultation, which has informed preparation of the proposal and decisions about the intervention, have been the content, presentation and acceptability of the intervention, best methods for recruiting to the trial, and the best way of engaging service users in the research process.

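### The recruitment and follow-up calendar does not fit into 30 months, and the option a) schedule in Appendix a cannot supply the 50 v 50 fallback analysis

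*Protocol*

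**What the plan says.** Four parts of the protocol set the calendar.

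- **Section 3, Project timetable.** The study lasts 30 months overall. "This involves a 15 month recruitment period in which we can realistically expect a rate of 3-4 participants randomised per month in each site"; at that pace the protocol counts on reaching its target of 50 at both centres. For follow-up, the same paragraph states: "Each participant will have a 9 month intervention and six month follow up", which is 15 months per person. Section 10 confirms assessments at baseline, 9 months and 15 months.
- **Section 13, Project timetable and milestones.** The first 3 months are set-up, and recruitment opens in month 4. The first phase recruits in months 4 to 9. "At month 30: the project data collection will finish".
- **Appendix a, 12-month review.** At least 40 participants are to be recruited, with a 3-month follow-up completed, by the end of year 1.
- **Appendix a, option a).** The team would carry on, "continuing to recruit a further 60 participants over the subsequent 18 months", while a funding decision is awaited. If the full trial is not funded, the data could still be analysed as a stand-alone external pilot, "comparing 50 versus 50 as originally planned".

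Section 8 makes complete-case analysis the primary analysis for the external pilot.

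**The concern.** Fifteen months of recruitment plus 15 months per participant fill 30 months exactly, so there is no room for a 3-month set-up inside the same 30 months. Separately, option a) runs recruitment up to the month in which data collection stops, so its later recruits cannot be followed to 9 months, let alone 15. Yet the same option presents the full 50 v 50 comparison as available without an extension.

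Participants cut off by the calendar would drop out of a complete-case primary analysis, and all of them would be late recruits. Section 7 also relies on 100 participants to describe outcome variability for a future power calculation, and a smaller sample does that less well.

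**Working it through.** **Inputs.** Study end: month 30 (Sections 3 and 13). Recruitment opens at elapsed month 3, the start of month 4 (Section 13). Recruitment length 15 months, 3 to 4 per site per month, two sites, target 100 (Section 3). Visits at 9 and 15 months (Section 10). Option a): 40 by month 12, then 60 over 18 months (Appendix a). The protocol gives no accrual curve, so even accrual is assumed.

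**The plan's own figure.** 15 months × 3 to 4 per site = 45 to 60 per site. Fifty per site needs 50/15 = 3.33 per month, so the recruitment target reproduces.

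**Rule.** A participant has the visit at *f* months by month 30 only if randomised by month 30 − *f*: month 21 for the 9-month visit, month 15 for the 15-month visit. Share lacking = (recruitment end − (30 − *f*)) / recruitment length.

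**Section 3 recruitment, opened as Section 13 says (elapsed months 3 to 18).**

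- Last 9-month visit: 18 + 9 = month 27, which fits.
- Last 15-month visit: 18 + 15 = month 33, which does not.
- Lacking 15-month data at 3.33 per site: (18 − 15)/15 = 20%, or 20 of 100.
- At 4 per site: 8 per month × 12 months = 96 randomised by month 15, so about 4 of 100 lack it.
- At 3 per site: 6 × 12 = 72 have it, and only 6 × 15 = 90 are recruited by month 18.
- If recruitment opened at the end of month 4 instead, the 20% would become (19 − 15)/15 = 26.7%.

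**Option a), 18 months counted from the 12-month review (months 12 to 30).**

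- Lacking 9-month data: (30 − 21)/18 = 50%, or 30 of 60.
- Lacking 15-month data: (30 − 15)/18 = 83%, or 50 of 60.
- The first 40, all in by month 12, reach 15 months by month 27 at the latest.
- Totals before dropout: 40 + 30 = 70 with 9-month data and 40 + 10 = 50 with 15-month data, or about 35 v 35 and 25 v 25.

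Sensitivity to when the 18 months begin:

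| Start | Recruitment ends | Lack 9-month data | Lack 15-month data |
|---|---|---|---|
| Month 9 | Month 27 | 6/18 = 33% | 12/18 = 67% |
| Month 12 | Month 30 | 9/18 = 50% | 15/18 = 83% |
| Month 14 | Month 32 | 11/18 = 61% | 17/18 = 94% |

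No start in this range removes the shortfall.

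**Which passage is out of line.** Forty in months 4 to 9 is 40/6/2 = 3.33 per site per month, the rate behind Section 3. Sixty more at that rate take 60/6.67 = 9 months and close at month 18. Option a) implies 60/18/2 = 1.67 per site per month.

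**Option b).** Its final 20 follow the month-24 check and are to be taken to the end of treatment. Nine months from month 24 is month 33.

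**Precision.** Interval width varies as 1/√n. Against 100, 70 participants widen it by √(100/70) = 1.20 and 50 by √(100/50) = 1.41.

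**The case against.** Several points on the other side are sound.

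- **The size depends on accrual.** At the upper end of the Section 3 rate only about 4 of 100 miss the 15-month visit. Appendix a says at least 40 by month 12, so 40 is a floor: 3 to 4 per site over elapsed months 3 to 12 would give 54 to 72. This is why ranges are shown. It does not move the month-33 last visit, which follows from a 15-month recruitment period whatever the accrual pattern.
- **An extension is foreseen.** It depends on funding, however, and the 50 v 50 fallback is offered for the case where funding is refused.
- **Shorter follow-up is partly foreseen.** Option b) takes its final 20 only to the end of treatment. That weakens any claim that 15-month data were promised for everyone in every branch, but it does not cure the 9-month shortfall.
- **This is a feasibility pilot.** There is no powered comparison, and a calendar cut-off is unrelated to randomised arm. The cost is precision, not bias between arms.

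Two stronger readings are tempting, and the protocol does not support them. A reader might infer that the 90% completeness criterion for the primary outcome cannot be met. Section 1 applies that criterion at 12 months, when nobody recruited from month 4 can have 15-month data, and it does not mention 15 months. A reader might also infer that Section 13 gives a third, conflicting accrual plan. Its months 4 to 9 cover the first phase only and match the Section 3 rate; the outlying accrual schedule is the one in option a).

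**Conclusion.** The point holds as an inconsistency in the calendar that should be fixed; it does not undermine the feasibility aims. There are two separate faults. The 3-month set-up pushes the last 15-month visit to month 33, three months past the end of data collection. This leaves about 20 of 100 without 15-month data under even accrual at the target rate, with everyone still able to reach 9 months. The option a) schedule goes further: at most about 70 of 100 have 9-month data and 50 of 100 have 15-month data at month 30, so its own no-extension comparison of 50 v 50 is not available at either visit.

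The counts rest on even accrual. The option a) counts also rest on exactly 40 in by month 12 and the 18 months starting then. That start is the natural reading, since 12 + 18 = 30. A month-9 start would raise the totals to 40 + 40 = 80 and 40 + 20 = 60, still short of 100. The conclusion does not depend on which visit is the primary time point.

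**What to change.** Adopt one schedule across Section 3, Section 13 and Appendix a.

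1. In Appendix a, option a), replace the 18-month recruitment period with recruitment closing at month 18: about 40 by month 9, then 60 over months 10 to 18 at 3.33 per site per month. Without an extension, recruitment should in no case run past month 21, the last entry that allows a 9-month visit by month 30.
2. State that closing at month 18 relies on about 40 being in by month 9. If 40 are reached only at month 12, it would need 60/6/2 = 5 per site per month, above the stated 3 to 4. Closing at month 21 would then need 60/9/2 = 3.33, but only about 40 + 20 = 60 would have 15-month data.
3. With closure at month 18, either move the end of data collection to month 33, or state that only those randomised by month 15 will have 15-month data: about 80, range about 72 to 96.
4. Reconcile the final 20 in option b) with the end of data collection in the same way.

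The cost is protocol wording, plus either three more months of follow-up visits or a smaller stated 15-month sample.
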